### Protocol Synopsis

Title	Clinical response to rhinovirus challenge in human asthmatics
Short Title	Clinical response to RV challenge in human asthmatics
Clinical Phase	Phase I clinical trial
Number of Sites	1. University of Virginia Health System, Charlottesville, VA
IND Sponsor/Number	[name]., University of Virginia / IND 15162
Study Objectives	
We hypothesize that the immune responses generated in the nose of asthmatics underlie subsequent systemic modulation of the immune system, and that – in susceptible individuals (i.e., those with pre-existing asthma) – this modified nasal milieu is responsible for the asthma exacerbation.
 
Primary Objective(s)
 
 
1. To determine whether RV increases expression of IL-25 transcripts by nasal epithelial cells in the asthmatic and AR but not control cohorts at the peak of infection (days 3 and 4).
 
2. To determine whether RV increases lower respiratory symptoms in the asthmatic but not AR and control cohorts.
 
3. To determine whether asthmatics and allergic rhinitics will demonstrate an increased severity of infection in comparison to control subjects.
 
 
Secondary Objective(s)
 
 
1. To determine whether asthmatic and AR cohorts demonstrate increased IL-25 transcript expression over the course of RV infection
 
2. To determine whether asthmatic and AR cohorts demonstrate increased expression of mRNA transcripts of a type 2 cytokine-inducing profile (IL-33 and TSLP).
 
3. To determine whether increased transcript expression of this type 2 cytokine-inducing profile can be corroborated as increased expression of protein.
 
4. To determine whether RV infection in the asthma cohort is associated with increases in biomarkers of inflammation.
 

	
 
5. To determine whether increased severity of RV infection in the asthma and AR cohorts will be associated with more symptoms.
 
6. To determine whether increased severity of RV infection in the asthma and AR cohorts is related to decreased innate immunity.
 

Study Design	Open label single center study in asthmatics as well as allergic rhinitic and healthy controls. All subjects will undergo GMP RV16 inoculation and responses will be compared between the 3 cohorts.
Primary Endpoint(s)	
 
1. RV-induced expression of IL-25 mRNA transcripts in the asthma and AR cohorts versus healthy controls as determined in nasal scraping samples obtained on days 3 and 4 (compared to day 0) as determined by qPCR.
 
2. RV-induced lower respiratory symptoms in the asthma cohort versus AR and healthy control as determined using modified Jackson scores (1) that will include cough, chest tightness, wheezing, and shortness of breath as well as via the asthma control test (ACT).
 
3. Severity of infection in the asthma and AR cohorts versus healthy controls as quantified by viral load present in nasal secretion samples as determined by qPCR performed on days 1, 2, 3, 4, 7.
 

Secondary Endpoint(s)	
 
1. IL-25 transcript expression in nasal scraping samples obtained on days 1, 2, and 7 (as compared to day 0).
 
2. Expression by nasal epithelial cells of a type 2 cytokine-inducing profile will be determined by also evaluating the time course of IL-33 and TSLP transcript expression by qPCR on nasal scraping samples obtained on days 0, 1, 2, 3, 4 and 7.
 
3. Expression of this type 2 cytokine-inducing profile will be corroborated by evaluating IL-25, IL-33, and TSLP protein expression by EIA on nasal secretion samples obtained via immunosorbent sponge.
 
4. Airway inflammation will be determined as increases in circulating absolute eosinophil counts, increased FeNO, and as changes in methacholine PD20.
 
5. Severity of RV infection will be corroborated as increases in upper respiratory symptoms using modified Jackson scores (1).
 

	
This scoring system includes sneezing, nasal discharge, nasal obstruction, sore throat, headache, malaise, and chills.
 
6. Severity of RV infection will be correlated with decreased innate immunity as assessed as reduced IFN-<math>\alpha</math>, -<math>\beta</math>, -<math>\lambda</math>, and IL-15 measured as qPCR of nasal scrapings and as enzyme immunoassays (EIAs) of nasal secretions (sponge-derived samples).

Accrual Objective	60 (20 each controls, AR, and asthma)
Study Duration	5 years to enroll, 8- 12 weeks for each participant to complete the study
Treatment Description	Rhinovirus (GMP RV16 HRV-16) inoculation
Inclusion Criteria	
All subjects:
 
 
1. Subjects must be able to understand and provide written informed consent.
 
2. Age 18 to <math>\leq</math>40 years of age, any gender, any racial/ethnic origin
 
3. Female subjects of childbearing potential must have a negative pregnancy test upon study entry (day -7) and before each procedure involving pharmacologic interventions (days 0, 4, and 7).
 
4. Female (and male) subjects with reproductive potential, must agree to use FDA approved methods of birth control for the duration of the study such as, but not limited to, birth control pills, contraceptive foam, diaphragm, IUD, abstinence, or condoms.
 
5. Participants must be willing to comply with study procedures and requirements.
 
6. Negative test for serum neutralizing antibody to RV16 at enrollment visit (<math><1:8</math>) (Visit 1).
 
7. Negative CoVID-19 test within 72 hrs of RV inoculation
 
8. Afebrile and negative CoVID screening questions on day of RV inoculation
 
 
Allergic Rhinitis Subjects
 
 
9. Allergy as determined by <math>\geq 1</math> positive prick skin test (wheal <math>\geq 5</math> mm diameter and 3mm larger than the diluent control) to Virginia inhalant panel within 5 years, and a history of symptoms of sneezing, rhinorrhea, pruritus, nasal congestion,
 

	
and/or allergic conjunctivitis on natural exposure to relevant allergens.
 
10. Negative methacholine challenge (less than 20% decline in FEV1 at <math>\leq 8</math>mg/ml) within 1 year
 
11. FEV1 <math>\geq 70\%</math> predicted or FEV1/FVC <math>\geq 80\%</math>.
 
12. No history of wheezing with viral infection in the last 6 years, and no use of rescue inhalers or long-term controllers for asthma in the last 6 years.
 
Allergic Asthmatic Subjects
 
13. Allergy as determined by <math>\geq 1</math> positive prick skin test (wheal <math>\geq 5</math> mm diameter and 3mm larger than the diluent control) to Virginia inhalant panel. Subjects are not required to have allergy symptoms at the time of study. Subjects will report history of symptoms of sneezing, rhinorrhea, pruritus, nasal congestion, and/or allergic conjunctivitis on natural exposure to relevant allergens.
 
14. Asthma determined by physician diagnosis and by a positive methacholine challenge (at least 20% fall in FEV1 at a methacholine concentration of <math>\leq 16</math> mg/ml) at screening protocol visit before enrollment (obtained within the past year).
 
15. Asthma must be controlled as determined by ACT score <math>\geq 20</math> and normal lung function (FEV1 <math>\geq 80\%</math> predicted and FEV1/FVC ratio <math>> 0.65</math>).

Exclusion Criteria (all subjects)
	
 
1. Positive test for serum neutralizing antibody to RV16 at enrollment visit (<math>\geq 1:8</math>) (Visit 1).
 
2. Upper airway modified Jackson criteria symptom scores <math>\geq 7</math> at time of inoculation.
 
3. Chronic heart disease including bradycardia, lung diseases other than asthma, or other chronic illnesses including epilepsy, peptic ulcer disease, thyroid disease, urinary tract infection, vagotonia, autoimmune disease, primary or secondary immunodeficiency or any household contacts who are known to be immune deficient. Any medical conditions that could be adversely affected by the administration of cholinergic agent.
 
4. Any use of LT modifiers, omalizumab, nasal corticosteroids within 4 weeks prior to Visit 1.
 

	
 
5. Current use of <math>\beta</math>-blockers or cholinesterase inhibitors (for myasthenia gravis)
 
6. <math>\beta</math>2-agonist use <math>\geq 4</math> days/week in any week or <math>\geq 2</math> nights during the month before Visit 1.
 
7. Recent (within 3-yr) asthma exacerbation requiring urgent care visit (unless the treatment involved only the use of a bronchodilator), hospitalization, or oral CCS
 
8. Intubation or management in the ICU for an asthma exacerbation ever.
 
9. An upper or lower respiratory tract infection within 2 months prior to enrollment.
 
10. Previous nasal or sinus surgery within the last 12 months
 
11. <math>>5</math> pack-year smoking history or any smoking within the past 6 mos.
 
12. Hemoglobin <math><11.5</math> g/dL for non-African American subjects or hemoglobin <math>< 11.0</math> g/dL for African American subjects detected at Visit 1.
 
13. Laboratory values (other than hemoglobin and ANC) measured at Visit 1 that are considered to be of clinical relevance by the Investigator.
 
14. Absolute neutrophil count (ANC) <math><1500</math> cells/mm^3 (or 1.5 K/<math>\mu</math>L) or absolute lymphocyte count (ALC) <math><800</math> cells/mm^3 detected at Visit 1.
 
15. Use of investigational drugs within 12 weeks of participation
 
16. Past or current medical problems or findings from physical examination or laboratory testing that are not listed above, which, in the opinion of the investigator, may pose additional risks from participation in the study, may interfere with the participant's ability to comply with study requirements or that may impact the quality or interpretation of the data obtained from the study.
 

Study Stopping Rules
	
The enrollment and dosing of RV-16 in the study may be suspended pending review by the NIAID DSMB and the University of Virginia IRB for the following reasons:
 
 
• Any subject has a severe asthma exacerbation that requires treatment in the emergency room or hospitalization
 
• <math>\geq 2</math> subjects experience severe asthma exacerbations requiring oral corticosteroids for <math>\geq 5</math> days, pending further expedited review.
 

	

• Any subject treated for pneumonia

• Any subject dies until expedited review is completed to determine whether the death might have resulted from any of the study procedures.

• Complications post biopsy requiring an urgent care visit in <math>\geq 2</math> subjects.

• Any death that occurs in the study, which is possibly or definitely related to study treatment regimen.

• The occurrence of a Grade 3 or higher related SAE in 2 or more of the study participants who have received a study treatment.

--	--

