### Primary Outcomes

1. RV-induced expression of IL-25 mRNA transcripts in the asthma and AR cohorts versus healthy controls as determined in nasal scraping samples obtained on days 3 and 4 (compared to day 0) as determined by qPCR.
2. RV-induced lower respiratory symptoms in the asthma cohort versus AR and healthy control as determined using modified Jackson scores (1) that will include cough, chest tightness, wheezing, and shortness of breath as well as via the asthma control test (ACT).
3. Severity of infection in the asthma and AR cohorts versus healthy controls as quantified by viral load present in nasal secretion samples as determined by qPCR performed on days 1, 2, 3, 4, 7

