### 3.2. Secondary Outcomes

1. IL-25 transcript expression in nasal scraping samples obtained on days 1, 2, and 7 (as compared to day 0).
2. Expression by nasal epithelial cells of a type 2 cytokine-inducing profile will be determined by also evaluating the time course of IL-33 and TSLP transcript expression by qPCR on nasal scraping samples obtained on days 0, 1, 2, 3, 4 and 7.
3. Expression of this type 2 cytokine-inducing profile will be corroborated by evaluating IL-25, IL-33, and TSLP protein expression by EIA on nasal secretion samples obtained via immunosorbent sponge.
4. Airway inflammation will be determined as increases in circulating absolute eosinophil counts, increased FeNO, and as changes in methacholine PD20.
5. Severity of RV infection will be corroborated as increases in upper respiratory symptoms using modified Jackson scores (1). This scoring system includes sneezing, nasal discharge, nasal obstruction, sore throat, headache, malaise, and chills.
6. Severity of RV infection will be correlated with decreased innate immunity as assessed as reduced IFN- $\alpha$ , - $\beta$ , - $\lambda$ , and IL-15 measured as qPCR of nasal scrapings and as enzyme immunoassays (EIAs) of nasal secretions (sponge-derived samples).

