#### 4.2. Inclusion Criteria

Individuals who meet all of the following criteria are eligible for enrollment as study participants. Participants in this trial will have participated in our separate (IRB protocol #12656 or 19512) screening protocol performed at day -28. Results obtained from the screening protocol will be used to initially determine eligibility as described below.

All subjects:

1. Subjects must be able to understand and provide written informed consent.
2. Age 18 to  $\leq 40$  years of age, any gender, any racial/ethnic origin
3. Female subjects of childbearing potential must have a negative pregnancy test upon study entry (day -7) and before each procedure involving pharmacologic interventions (days 0, 4, and 7).
4. Female (and male) subjects with reproductive potential, must agree to use FDA approved methods of birth control for the duration of the study such as, but not limited to, birth control pills, contraceptive foam, diaphragm, IUD, abstinence, or condoms.
5. Participants must be willing to comply with study procedures and requirements.
6. Negative test for serum neutralizing antibody to RV16 at enrollment visit ( $<1:8$ ) (Visit 1).
7. Negative CoVID-19 test within 72 hrs of RV inoculation
8. Afebrile and negative CoVID screening questions on day of RV inoculation

Allergic Rhinitis Subjects:

1. Allergy as determined by  $\geq 1$  positive prick skin test (wheal  $\geq 5$  mm diameter and 3mm larger than the diluent control) to Virginia inhalant panel within 5 years (done as part of screening protocol), and a history of symptoms of sneezing, rhinorrhea, pruritus, nasal congestion, and/or allergic conjunctivitis on natural exposure to relevant allergens.
2. Negative methacholine challenge (less than 20% decline in FEV1 at  $\leq 8$ mg/ml) within 1 year
3. FEV1  $\geq 70\%$  predicted or FEV1/FVC  $\geq 80\%$ .
4. No history of wheezing with viral infection in the last 6 years, and no use of rescue inhalers or long-term controllers for asthma in the last 6 years.

Allergic Asthmatic Subjects:

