***Analysis of circulating eosinophil count:*** Changes in the absolute eosinophil count (AEC) from day -7 to post-challenge day 4 will be compared between the 3 different groups via ANOVA. ***Model specification:*** The primary source of  $\Delta$  AEC variation that will be examined will be the variation due to study-group to study-group variation. ***Hypothesis testing:*** We will test if the 3 underlying study-population  $\Delta$  AEC distributions share the same mean. A  $p \leq 0.05$  decision rule will be utilized as the null hypothesis rejection rule for this test. If rejected a Bonferroni corrected two-sided  $p \leq 0.05/3$  decision rule will be utilized as the null hypothesis rejection rule for between-group comparisons. ***Alternative analytical approach:*** If the ANOVA model assumptions are violated, the  $\Delta$  %EC data will be analyzed by *distribution-free* permutation methods.

***Analysis of eosinophil percent of total cells:*** Changes in the eosinophil percent of total cells ( $\Delta$  %EC) from day -7 to post-challenge day 4 will be compared between the 3 different groups via ANOVA. ***Model specification:*** The primary source of  $\Delta$  %EC variation that will be examined will be the variation due to study-group to study-group variation. ***Hypothesis testing:*** We will test if the 3 underlying study-population  $\Delta$  %EC distributions share the same mean. A  $p \leq 0.05$  decision rule will be utilized as the null hypothesis rejection rule for this test. If rejected a Bonferroni corrected two-sided  $p \leq 0.05/3$  decision rule will be utilized as the null hypothesis rejection rule for between-group comparisons. ***Alternative analytical approach:*** If the ANOVA model assumptions are violated, the  $\Delta$  %EC data will be analyzed by *distribution-free* permutation methods.

***Analysis of upper respiratory symptom scores:*** The upper respiratory symptom scores that will be reported daily from challenge study day 0 to challenge study day 7, will be analyzed in two ways. In the first approach, cumulative upper respiratory total symptom (CURTS) will be computed for challenge days 0 to 4, and for challenge days 0 to 7. In the second approach the daily total upper respiratory symptom scores will be analyzed. *Please see the analytical plan for the analysis lower respiratory symptom scores for further details (section 13.4.2).*

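### Secondary objective 5 has no named analysis of viral load against upper symptoms, and the cohort comparison of symptoms that stands in for it takes no account of day-0 scores

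*Combined protocol and SAP*

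**What the plan says.** Secondary objective 5 (Synopsis and section 2.2) is: "To determine whether increased severity of RV infection in the asthma and AR cohorts will be associated with more symptoms". Severity has its own definition in primary outcome 3: "Severity of infection in the asthma and AR cohorts versus healthy controls as quantified by viral load present in nasal secretion samples". The endpoint listed under the same number uses symptoms as a second indicator of severity: "Severity of RV infection will be corroborated as increases in upper respiratory symptoms using modified Jackson scores". The score is described in section 3.2: "This scoring system includes sneezing, nasal discharge, nasal obstruction, sore throat, headache, malaise, and chills".

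Section 13.4.4 analyses upper symptoms in two ways. In the first, "cumulative upper respiratory total symptom (CURTS) will be computed for challenge days 0 to 4, and for challenge days 0 to 7"; in the second, daily totals are analysed. For details it refers to the lower-symptom plan in 13.4.2. There, both negative-binomial GEE models have two predictors: study group and challenge period for the cumulative score, and study group and study day for the daily score.

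AR subjects enter with "a history of symptoms of sneezing, rhinorrhea, pruritus, nasal congestion, and/or allergic conjunctivitis on natural exposure to relevant allergens" (section 4.2). Asthmatic subjects report the same kind of history.

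**The concern.** The objective asks about an association between load and symptoms. The specified models estimate differences in symptoms between cohorts and contain no load term. If symptoms follow load within every cohort but mean load is similar across cohorts, these models would not reveal it.

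A cohort difference in symptoms also has another possible source. Three of the seven scored items (sneezing, nasal discharge, nasal obstruction) overlap with the nasal symptoms in the allergic cohorts' entry criteria. Inoculation is withheld only at an upper score of 7 or more (sections 4.3 and 8.2), so day-0 scores of 0 to 6 are admitted. Antihistamines are prohibited (section 7.3). Stable rhinitis is then counted on every scored day, including day 0, and nothing in the between-cohort model removes it. What is at stake is the answer to one listed secondary objective and the use of symptoms to support the primary severity result.

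**Working it through.** **1. Is load paired with symptoms anywhere?**
- 13.4.2, applied to upper symptoms by 13.4.4: predictors are group and period, or group and day. No load.
- 13.4.4, bivariate correlations: the two examples pair cumulative load with IL-25/IL-33/TSLP and with the interferons and IL-15. Symptoms are not mentioned.
- 13.4.4, albuterol: load and symptoms are both predictors, and the outcome is inhaler use.
- 13.6: pre/post tests within each cohort for every secondary outcome. These do not involve load.
- Objective 6, worded in parallel, has a correlation endpoint and a named load correlation. Objective 5 has neither.

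**2. Is day 0 handled?** The IL-25, FEV1, FeNO and interferon/IL-15 models all adjust for the day-0 value. The upper-symptom models do not, and CURTS adds day 0 into the sum.

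**3. Nearest stated figure.** The plan gives no power for objective 5. For load itself it gives a detectable ratio of 25 (SD 1.32, 20 per group, two-sided 0.05/3, power 0.80). A two-sample t-test gives 25.4, and power 0.796 at a ratio of 25, so that figure is reproduced.

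**4. How much can rhinitis contribute?** CURTS for days 0 to 4 sums five daily scores, so a stable b points a day adds 5b; at the admitted ceiling, 5 × 6 = 30. If infection is the same in AR and controls and its CURTS mean is m, the AR-to-control ratio is (m + 5b)/m. The rejection probabilities below are simulated (20 per group, gamma-Poisson CURTS with CV 0.6, log-ratio Wald test with robust SE at 0.05/3). The values of m, CV and b are assumptions.

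| b (points/day) | 5b | Ratio, m = 15 | Rejects | Ratio, m = 30 | Rejects |
|---|---|---|---|---|---|
| 0.5 | 2.5 | 1.17 | 0.08 | 1.08 | 0.04 |
| 1 | 5 | 1.33 | 0.21 | 1.17 | 0.08 |
| 2 | 10 | 1.67 | 0.67 | 1.33 | 0.24 |
| 3 | 15 | 2.00 | 0.94 | 1.50 | 0.48 |

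With no rhinitis the test rejects in about 2 to 3% of runs.

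A second simulation let rhinitis vary between subjects and dropped anyone scoring 7 or more on day 0. At 1, 2 and 3 points a day, the unadjusted test rejected in 34%, 79% and 95% of runs (m = 10) and in 10%, 31% and 57% (m = 20). A test on change from day 0 rejected in 1.3 to 1.9% throughout.

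**5. What could a load-symptom analysis detect?** With the Fisher z approximation, detectable rho = tanh[(1.960 + 0.842) × √(1.06/(N − 3))] at two-sided 0.05 and power 0.80:
- N = 60: tanh(2.802 × 0.1364) = 0.36
- N = 40 (asthma and AR): tanh(2.802 × 0.1693) = 0.44
- N = 20 (one cohort): tanh(2.802 × 0.2497) = 0.60

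At 0.05/3 these become 0.41, 0.50 and 0.67.

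**The case against.** A reader might infer that the plan only compares cohorts and cannot show the link at all. The documents do not support that. Section 13.6 adds within-cohort pre/post tests, and the correlation clause in 13.4.4 is open-ended: its two pairs are given as examples, so load against symptoms is unnamed but not excluded. What stands against this defence is that an unnamed pair is not prespecified, and a pooled Spearman correlation would adjust for neither cohort nor day 0.

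A reader might also infer that the trial would report more severe infection in AR when there is only rhinitis. That goes too far. Severity is defined by load, so a raised CURTS would sit beside a null load result, and the daily model would show a day-0 difference if there were one. The narrower point remains: the endpoint calls the symptom increase corroboration, and the contrast as specified cannot separate the two sources.

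Objective 5 can also be read at cohort level, as asking whether cohorts with more severe infection have more symptoms. That reading is fair and fits the endpoint, but it still needs a contrast free of pre-existing rhinitis.

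Two features limit the bias. The cut-off of 7 caps the day-0 score. Section 1.3 describes challenges done outside periods of high allergen exposure, although sections 4 and 8 contain no such rule. At 0.5 points a day the effect is small.

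**Conclusion.** The concern holds in this form: no load-symptom analysis is named for objective 5, and the between-cohort upper-symptom models ignore day-0 scores, unlike the plan's other repeated-measures models with a day-0 baseline. Both follow from the text without assumptions.

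The size of the rhinitis effect does rest on assumptions, because the documents give no CURTS mean, spread or day-0 score. Over the range examined it runs from close to the error rate (0.04) to near-certain rejection (0.94). The direction is secure for any stable excess of day-0 symptoms in the allergic cohorts. The simulations compare AR with controls; the asthma cohort shares the nasal history, so its contrast with controls is exposed in the same way.

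This affects one of six secondary objectives and the supporting evidence for a primary one. It does not affect the viral-load analysis itself.

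**What to change.** (a) For objective 5, specify a negative-binomial regression of the upper symptom score summed over days 1 to 4 on log10 cumulative RV load, with cohort and day-0 upper score as covariates. State in advance whether it uses all 60 subjects or the 40 named in the objective. Report the load-by-cohort term descriptively: its power is only about 0.14 to 0.36 when the correlation is 0.3 to 0.5 in two cohorts and zero in the third.

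(b) Leave day 0 out of the CURTS sum and add the day-0 upper score as a covariate in the between-cohort CURTS and daily upper-symptom models. A single day-0 score is a noisy measure of stable rhinitis, so the covariate will reduce the bias without necessarily removing all of it. Reporting the change-from-day-0 comparison alongside is a useful check.

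(c) Endpoint 5 can stay, provided that corroboration rests on the day-0-adjusted contrast read together with the viral-load result.

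(d) State which days enter the longer sum. Section 13.4.4 describes daily reporting from day 0 to day 7, whereas the cross-referenced plan in 13.4.2 uses days 0 to 4 and 7.

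The cost is one extra model and some SAP wording, with no new data. The association analysis will detect only moderate to strong correlations, and the plan should say so.
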